6. STATISTICAL CONSIDERATIONS AND ANALYSIS PLAN

All efficacy analyses will be conducted according to the intent-to-treat principle and will include all patients who meet the following condition with patients allocated to the treatment arm to which they were randomized:

- Randomized patients who have confirmed influenza A infection as confirmed by a central PCR test from Day 1 samples

Safety analyses will include all patients who were included in the randomization and who received at least one dose of study medication, with patients allocated to the treatment arm associated with the regimen actually received.

No formal hypothesis testing will be done in this study. As a result, no adjustment for a type 1 error will be made to account for the multiplicity of analyses.

Final efficacy and safety analyses of the total study population will be conducted at the end of the study after all patients have completed all study assessments and the database has been cleaned and closed. Further details of the analyses, including analysis of the exploratory endpoints, will be contained in the statistical analysis plan

(SAP) which will be prepared and finalized before the first optional interim analysis (see [Section 6.7](#)) or the final efficacy and safety analysis, if no interim analysis takes place.

6.1 DETERMINATION OF SAMPLE SIZE

The purpose of this study is estimation of the effect size and hypothesis generation regarding the effect of MHAA4549A on the time to normalization of respiratory function relative to the standard of care rather than hypothesis testing. Point and interval estimates will be obtained. A total of 334 patients will be enrolled in this study in order to obtain approximately 300 evaluable patients (an estimated dropout rate of 10%). It is assumed that the median time to normalization of respiratory function in the control arm is 5 days. This sample size (approximately 150 patients per arm) provides 75% power to detect a treatment difference of 1 day for the primary endpoint assuming a 2-sided alpha of 0.2.

Operating characteristics (power) under other possible assumptions for 2-sided alpha of 0.05 and true differences of 1 to 2 days are provided in [Table 7](#).

Table 7 Operating Characteristics for Proposed Study Design for Several Possible True Underlying Median Values

	True Underlying Median for MHAA4549A		
	3 days	3.5 days	4 days
Hazard Ratio	0.60	0.70	0.80
Power of log-rank test ^a	99%	86%	48%
95% confidence interval for true hazard ratio ^b	(0.48, 0.75)	(0.56, 0.88)	(0.64, 1.00)

Note: Operating characteristics are based on the following assumptions: 300 evaluable patients, event times are exponentially distributed, median time to normalization of respiratory function in the control arm is 5 days, and patients are followed for 60 days.

^a Two-sided $\alpha=0.05$.

^b Confidence intervals are based on the assumption that the point estimate is equal to the true underlying value of the hazard ratio in each column.

It should be noted that the study is underpowered for detection of minimally clinically meaningful differences at a 2-sided alpha of 0.05 such as a true hazard ratio of 0.80 (see third column of [Table 7](#)).

6.2 SUMMARIES OF CONDUCT OF STUDY

The number of patients who enroll, discontinue (early discontinuation of treatment or early termination from the study), and complete the study will be tabulated by treatment group using descriptive statistics. Reasons for early discontinuation of treatment or early termination from the study will be listed and summarized by treatment group. Any eligibility criteria exceptions and other protocol deviations will also be summarized by treatment group.

6.3 SUMMARIES OF TREATMENT GROUP COMPARABILITY

Demographic and baseline characteristics of the patient will be summarized for all randomized patients by treatment group by use of descriptive statistics. Baseline is defined as the last available value prior to study drug administration.

During the study; patient disposition, concurrent treatment, and compliance with study treatment and visits will be summarized on the safety analysis population using descriptive statistics.

6.4 EFFICACY ANALYSES

The primary and secondary efficacy analyses will include all randomized patients who are confirmed to be influenza A infected, with patients grouped according to the treatment assigned at randomization.

Time to event data will be computed using Kaplan-Meier methodology and stratified Cox proportional hazards models and will be summarized using n, median when estimable, hazard ratios, and 95% confidence intervals. Patients who are lost to follow-up (while event free) will be censored at the time that they are last known to be event free.

Estimation of the treatment difference of proportions and its 95% confidence interval will be calculated using stratum-adjusted Mantel-Haenszel methodology ([Koch et al. 1989](#)). For continuous endpoints, Analysis of Covariance methods (after appropriate transformation of data) will be used to estimate treatment differences and 95% confidence intervals.

Other than censoring in the time to event analyses, no other imputation for missing data will be performed.

6.4.1 Primary Efficacy Endpoint

- Median time to normalization of respiratory function

6.4.2 Secondary Efficacy Endpoints

- Proportion of patients with clinical failure after 24 hours post-infusion of study drug
- Median time to clinical resolution of vital signs
- Hazard ratio for mortality at Day 14, Day 30, and Day 60
- Mean and median AUC of viral load
- Mean and median peak viral load
- Median duration of viral shedding in upper respiratory samples
- Median duration of hospitalization
- Median duration of ICU stay
- Proportion of patients requiring antibiotics for respiratory indications during study

- Proportion of patients with influenza secondary complications
- Median duration of ventilation
- Proportion of patients who are readmitted by Day 30 and Day 60

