3.3.3 Secondary Efficacy Outcome Measures

The secondary efficacy outcome measures for this study are as follows:

- Clinical failure after 24 hours post-infusion of study drug; defined as:
 - Progression to increased O₂ requirement defined by an increase in oxygen supplementation from low flow oxygen (2–6 L/min) to high flow oxygen (>6 L/min) or from oxygen supplementation alone to any PPV
 - Progression to ICU
 - Prolonged ventilation or O₂ support defined by >2 weeks, or
 - Death
- Time to clinical normalization of vital signs (3/5 criteria must be met):
 - SpO₂ > 95% without supplemental O₂ for at least 24 hours
 - Core temperature < 37.2°C immediately prior to receipt of any antipyretic drug, and at least 6-8 hours from the last dose of antipyretic or core temperature >36°C in patients who are initially hypothermic
 - Heart rate (HR) < 100/minute
 - Systolic blood pressure (SBP) > 90 mmHg
- All-cause mortality at Day 14, Day 30, and Day 60
- Influenza A viral load in nasopharyngeal samples
 - AUEC
 - Peak viral load

- Time to resolution of infection
- Duration of hospitalization
- Duration of ICU stay
- Antibiotic usage for respiratory infections
- Complications of influenza:
 - Pneumonia (HAP/VAP)
 - Exacerbations of chronic lung disease
 - Myocarditis
 - ARDS
 - Otitis media
 - Other related complications
- All-cause readmission at Day 30 and Day 60
- Duration of ventilation

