4.6.2 Diagnostic Testing for Enrollment

All hospitalized patients with severe influenza A will be assessed for disease confirmation and enrollment into the study. A Sponsor-supplied rapid influenza test is required for the diagnosis of influenza A infection and uses a nasopharyngeal swab. When the Sponsor-supplied rapid influenza test is negative, the study inclusion criteria can be satisfied with a positive local molecular test (PCR) if the result is within the 48-hour screening window. Patients may be enrolled based on a positive local molecular test (PCR) result within the 48-hour screening window, but the rapid influenza test must still be conducted prior to randomization. Other tests may not be used for enrollment in the study unless the Sponsor has reviewed and approved the use of the diagnostic.

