6.4.3 Subgroup Analyses

Subgroup analyses will be performed to examine the consistency of the treatment estimates with use of the primary and selected secondary endpoints. Subgroups will include the stratification factors as well as patients who are identified at baseline as influenza A positive by the upper, lower, or both airways and by patients with bacterial co-infections at admission. Additional subgroups may be added following assessment of baseline characteristics as exploratory analyses.

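### The nasopharyngeal viral endpoints are analysed in all PCR-confirmed patients, so any who are positive only in the lower airway dilute the estimated antiviral effect

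*Combined protocol and SAP*

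**What the plan says.** Section 6 defines one set for all efficacy analyses: "Randomized patients who have confirmed influenza A infection as confirmed by a central PCR test from Day 1 samples". It does not say which airway the sample comes from. Section 6.4 applies this set throughout: "The primary and secondary efficacy analyses will include all randomized patients who are confirmed to be influenza A infected".

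The virology outcomes are confined to the upper airway. Section 3.3.3 lists "Influenza A viral load in nasopharyngeal samples", with AUEC, peak and time to resolution beneath it. Section 6.4.2 adds "Median duration of viral shedding in upper respiratory samples", and gives AUC and peak as both means and medians.

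Section 6.4.3 plans subgroups that include "patients who are identified at baseline as influenza A positive by the upper, lower, or both airways", "with use of the primary and selected secondary endpoints". The selected endpoints are not named.

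On entry, Section 4.6.2 says: "A Sponsor-supplied rapid influenza test is required for the diagnosis of influenza A infection and uses a nasopharyngeal swab". It also allows a second route: "Patients may be enrolled based on a positive local molecular test (PCR) result within the 48-hour screening window". The specimen for the local PCR is not stated.

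Continuous endpoints are to be analysed by ANCOVA after a transformation; neither the covariates nor the transformation is named. Apart from censoring, Section 6.4 allows no imputation. Section 6 defers further detail to a SAP that is not in the supplied text.

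**The concern.** The analysis set and the measurement do not match. A patient can enter the set on a lower-airway sample, yet the endpoint is read from NP samples only. Such a patient has no NP virus at baseline for treatment to clear. If scored near zero, the patient adds nothing to the between-arm difference but counts in the denominator. For duration of shedding, a patient who is never NP-positive has no defined value, and the plan does not say whether that patient counts as zero days or is left out.

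These endpoints are the trial's direct clinical evidence of antiviral activity, and Section 3.2.4 justifies the 3600 mg dose partly by reductions in upper-airway shedding. Section 6.1 describes the study as one of estimation, so a diluted estimate is itself the harm; no hypothesis test has to fail for it to matter.

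**Working it through.** **The plan's own figures.** The protocol gives no precision or power figure for the viral endpoints. Its sample-size figures concern the primary endpoint, and they reproduce. With 300 events, power = Φ(√300/2 × |ln HR| − 1.96) gives 99.3%, 87.1% and 48.9% for hazard ratios 0.60, 0.70 and 0.80, against 99%, 86% and 48% in Table 7. At two-sided alpha 0.2 and hazard ratio 0.80 the same formula with 1.2816 gives 74.2%, against 75%. Enrolment is 300/0.9, rounded up to 334. Only the 150 per arm is carried forward.

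**Assumptions, none of them in the documents.** A share p of each arm is positive only in the lower airway (5%, 10% and 20% shown) and is scored 0. Among NP-positive patients, AUEC has mean 300 against 240 and SD 120 in both arms.

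**1. Mean difference.** Averaging over the full set gives (1−p) × 60: 57, 54 and 48.

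**2. Precision without adjustment for baseline.** The variance in an arm with NP-positive mean μ is (1−p) × 120² + p(1−p) × μ². At p = 10% this is 12,960 + 8,100 = 21,060 and 12,960 + 5,184 = 18,144, so z = 54/√(39,204/150) = 3.34. In NP-positive patients only, z = 60/(120 × √(2/135)) = 4.11.

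**3. Precision with adjustment for baseline NP status.** The between-cluster term is then removed. A main-effects model leaves a residual variance of (1−p) × 120² + p(1−p) × 60²/4, and z = (1−p) × 60/√(2 × variance/150). At p = 10% the variance is 12,960 + 81 = 13,041 and z = 4.10. Simulation of the same model agreed to within about 0.03.

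| p | Mean difference | z, all, unadjusted | z, all, adjusted for NP status | z, NP-positive only | Information kept, unadjusted |
|---|---|---|---|---|---|
| 5% | 57 | 3.77 | 4.21 | 4.22 | 80% |
| 10% | 54 | 3.34 | 4.10 | 4.11 | 66% |
| 20% | 48 | 2.72 | 3.85 | 3.87 | 49% |

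The last column is the squared ratio of the unadjusted z to the NP-positive z. Adjustment recovers nearly all the precision, but the estimate itself stays at 57, 54 or 48.

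**4. Median AUEC.** The median of the mixture sits at the (0.5−p)/(1−p) quantile of the NP-positive distribution. With equal SDs both arms move down equally: at p = 20% the medians are 261.8 and 201.8, still 60 apart. This depends on the shift model.

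**5. Shedding duration.** Assume exponential durations with medians of 5 and 3.6 days in NP-positive patients. The mixture median is m × [1 + log₂(1−p)], so the 1.4-day difference becomes 1.30, 1.19 and 0.95 days. A simulation of 600 trials per share, with durations rounded up to whole days, gave 1.29, 1.20 and 0.99. Its hazard ratio for cessation, all patients against NP-positive only, was about 1.40 against 1.43, 1.38 against 1.44, and 1.34 against 1.44. The simulation returned 1.44 with no zeros at all, so these pairs should be read against each other and not as absolute values.

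**The case against.** The strongest objection is to the size. A reader might infer from the unadjusted column that 20% to 51% of the information is lost. The documents do not support that: Section 6.4 specifies ANCOVA, and adjusting for baseline NP status removes almost all of that loss. The covariates are not named, so this recovery is an assumption as well, but it means the precision argument cannot carry the point. The median AUEC difference is also unmoved under the shift model. Both parts of this objection stand.

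A reader might also infer that lower-airway-only patients are structural zeros who hide an antiviral effect. No scoring rule is given, and Appendix 1a schedules NP samples daily to Day 10 and at later visits, so a patient negative on Day 1 could turn positive. Nor is a negative rapid NP test followed by a positive local PCR proof that NP virus is absent, since the PCR specimen may itself be an NP swab. The 45% cap on patients receiving positive pressure ventilation is nowhere linked to lower-only positivity. The share could be near zero.

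The airway subgroups in Section 6.4.3 are partial mitigation. They do not settle the matter, because they are consistency checks on unnamed secondary endpoints and leave the main viral analysis in the full set.

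Finally, the statistical text supplied is Version 3 and earlier. Version 5 adds an 8400 mg arm, but its statistical section and the SAP are not in the supplied text, and some sampling footnotes are redacted. The gap is therefore shown only for the text supplied.

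**Conclusion.** The point holds in a limited form. As written, the plan averages upper-airway viral endpoints over a set that can include patients with no upper-airway virus at baseline, and it gives no rule for scoring them. If they are scored near zero, the mean difference is multiplied by (1−p), a reduction of 5%, 10% or 20% at those shares, and the effect on shedding duration is attenuated as well. This rests on an unstated share and an unstated scoring rule. At 5% the dilution is modest; at 20% it would matter for an estimate meant to inform later development. Additional loss of precision arises only if the analysis does not adjust for baseline NP status or load.

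The documents do not show that an effect would be concealed. There is no formal testing, and even the unadjusted 20% case above leaves z at 2.72. This is an inexpensive improvement to secondary endpoints, with no bearing on the primary analysis.

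**What to change.** In Section 6.4.2, or in the SAP:

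- Make the main analysis of NP AUEC, NP peak, time to resolution and duration of upper-airway shedding the confirmed patients whose pre-dose Day 1 NP sample is positive by central PCR.
- Name Day 1 NP viral load as the ANCOVA covariate for the continuous endpoints.
- State how negative and below-limit values are scored, including shedding duration in a patient who is never NP-positive.
- Keep the full confirmed set as a supportive analysis, and report the number of lower-airway-only patients by arm.

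The restriction uses a pre-dose value, so the randomised comparison is preserved. Appendix 1a already schedules an NP sample on Day 1, before dosing unless otherwise indicated. The cost is a change of wording and a somewhat smaller n: at p = 10%, 135 instead of 150 per arm. The result then applies to patients with upper-airway virus at baseline, which is why the full set should stay alongside. The sponsor should first confirm that the Version 5 protocol and the SAP do not already contain this.

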2.3 SECONDARY EFFICACY OBJECTIVES

The secondary efficacy objectives for this study are as follows:

- To measure clinical failure, as defined in [Section 3.3.3](#), after 24 hours post-infusion of study drug
- To determine the time to clinical resolution of vital signs
- To measure mortality in patients
- To determine changes in the extent and duration of viral shedding in upper respiratory samples
- To measure the duration of hospital and/or ICU stay
- To measure antibiotic usage for respiratory indications

- To measure the frequency and severity of the following secondary complications of influenza:
 - Pneumonia (hospital acquired pneumonia [HAP]/ ventilator acquired pneumonia [VAP])
 - Exacerbations of chronic lung disease
 - Myocarditis
 - Acute respiratory distress syndrome (ARDS)
 - Otitis media
 - Other related complications
 - Readmission rates at 30 and 60 days after study treatment
- To measure duration of PPV
- To measure readmission rates

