3. STUDY DESIGN

3.1 DESCRIPTION OF THE STUDY

3.1.1 Overview of Study Design

This is a Phase 2b, randomized, double-blind, placebo-controlled study designed to assess the safety and clinical activity of a single intravenous (IV) dose of MHAA4549A in hospitalized patients with severe influenza A in combination with oseltamivir versus a comparator arm of placebo with oseltamivir. This study is planned to take place in approximately 170 study centers globally.

Patients will be randomized 1:1 into two treatment groups: a single IV dose of 3600 mg of MHAA4549A with oseltamivir or a single IV dose of placebo with oseltamivir. All patients will receive oseltamivir, a NAI, as standard therapy for a minimum of 5 days after study drug administration. Oseltamivir at doses of 75 mg BID or 150 mg BID is permitted in order to be consistent with local standard of care practice. Treatment for longer than 5 days is permitted based on local investigator discretion. The patient must start Sponsor-supplied oseltamivir within 8 hours of study drug administration. The study has a planned enrollment of approximately 334 patients globally.

Hospitalized patients with an O₂ or PPV requirement will be evaluated for influenza A infection. Enrollment in this study requires ongoing treatment within 24 hours of hospital admission with one of the following:

- any PPV or
- any supplemental O₂ to maintain oxygen saturation (SpO₂) >92% (see [Section 3.3.2](#))

Patients on PPV should not exceed 45% of the total patients enrolled.

A Sponsor-supplied rapid influenza test and/or a local polymerase chain reaction (PCR) test must be used as an aid in the diagnosis of influenza A infection.

At the time of randomization, patients who are eligible for enrollment, as described above, will be randomized to receive MHAA4549A at a dose of 3600 mg or placebo. Patients will be stratified by site, PPV versus supplemental O₂ at randomization, and suspected or confirmed bacterial pneumonia versus no bacterial pneumonia based on the status at randomization.

[figure not shown]
Eligible patients who are enrolled into the study will receive either a single IV infusion of MHAA4549A or a single IV infusion of placebo on Day 1. All patients must have the study drug infused within 48 hours of hospital admission or sooner if possible. All patients will receive oseltamivir for a minimum of 5 days (10 doses), starting on Day 1, beginning no later than 8 hours after study drug administration.

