3.2.2 Rationale for Patient Population and Primary Endpoint

Severe influenza, for the purpose of this study, is defined as requiring one of the following treatments: any supplemental O₂ to maintain an SpO₂ > 92% or PPV. PPV is defined as any mechanical positive pressure device to maintain oxygenation; this can include positive pressure mask and intubation. A Sponsor-supplied rapid influenza test and/or a local PCR must be used as an aid in the diagnosis of influenza A infection.

This patient population was chosen based on the rationale that respiratory failure is a hallmark of influenza and a major driver of morbidity and mortality, as well as hospitalization. The recovery from ventilator support has been shown to be directly proportional to time spent in the ICU ([Blackwood 2011](#); [PREMIER[®] database](#)). Based upon an analysis of morbidity and mortality, the patient population that requires supplemental O₂ or ventilation on their first day of admission was determined to have a high unmet medical need as they have an estimated mortality of 9%–32%, and 27% require admission to the ICU, according to analysis of a database of over 70,000 hospitalized patients in the US from 2005–2012 ([PREMIER[®] database](#)).

Support for use of the respiratory endpoint in this population comes from recently published data demonstrating that a composite endpoint that captured respiratory rate, fever, heart rate, and blood pressure resolution was primarily driven by the respiratory component of the endpoint ([Marty et al. 2014](#)).

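### The planned median durations of ventilation and ICU stay have no stated denominator or value for non-users, and neither natural reading gives a useful comparison between arms

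*Combined protocol and SAP*

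**What the plan says.** Two secondary objectives in Section 2.3 are "To measure duration of PPV" and "To measure the duration of hospital and/or ICU stay". Section 6.4.2 turns them into "Median duration of ventilation" and "Median duration of ICU stay".

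The analysis set is in Section 6.4: "The primary and secondary efficacy analyses will include all randomized patients who are confirmed to be influenza A infected". No section gives a separate denominator for the two durations, a value for patients who never used the support, or a rule for patients who die on it. Nor is it said whether the durations are time-to-event or continuous endpoints.

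Two other figures bear on the point. Section 3.1.1 states: "Patients on PPV should not exceed 45% of the total patients enrolled". Section 3.2.2 reports from a hospital database that, of patients on oxygen or ventilation on the first day of admission, "27% require admission to the ICU". Section 3.3.3 counts a move from oxygen to PPV, and a move to ICU, as clinical failure, so both are expected to occur after randomization.

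**The concern.** A median over a whole arm describes duration only if at least half the arm used the support. By design at least 55% of patients enter without PPV, and the only ICU rate the protocol gives for this kind of patient is 27%. Following Section 6.4 literally, with non-users at 0 days, can therefore return 0 against 0, or a contrast set by which arm happened to pass the halfway mark.

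Restricting to users avoids the zeros but brings a different problem. Treatment may change who is ventilated or enters ICU. If the drug keeps milder patients off support, sicker patients remain in its subset and its median can lengthen. At stake is whether two stated objectives yield an interpretable comparison of randomized arms.

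**Working it through.** **The plan's own figures.** The documents give no expected value, usage rate or power for these two medians. The design figures that Section 6.1 does give reproduce:

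- Enrolment: 300 / 0.9 = 333.3, rounded up to 334.
- Log-rank power with D = 300 events, Φ(√D·|ln HR|/2 − 1.96): 99.3%, 87.0% and 48.9% at HR 0.60, 0.70 and 0.80, against the stated 99%, 86% and 48%.
- At HR 0.80 and two-sided alpha 0.2: 74.2%, against 75%.

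**Inputs for the check.**

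- About 150 evaluable patients per arm (Section 6.1).
- b, the share on PPV at entry: at most 45% (Section 3.1.1).
- q, the share of oxygen patients who later need PPV: no rate is given, so a range is shown.
- ICU use: 27% (Section 3.2.2, background figure).

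**Reading 1: all patients, non-users at 0 days (an assumption).** With 150 per arm, the median is 0 if fewer than 75 patients used the support.

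*ICU.* At 27%, about 0.27 × 150 = 40.5 patients per arm are expected in ICU. The binomial probability of 75 or more is 1.8 × 10⁻⁹, so the median is 0 in every arm.

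The 27% could be low for this trial. At the PPV cap, if all PPV patients were in ICU (assumption), use would already be 45%, and ICU entry by (0.50 − 0.45)/0.55 = 9.1% of oxygen patients would bring it to 50%. If 75% of them were in ICU, the oxygen patients' rate would have to be (0.50 − 0.3375)/0.55 = 29.5%.

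*Ventilation.* The share ever ventilated is b + (1 − b)q, which reaches 50% when q = (0.5 − b)/(1 − b):

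| PPV at entry, b | Break-even q |
|---|---|
| 45% (cap) | 0.05/0.55 = 9.1% |
| 40% | 0.10/0.60 = 16.7% |
| 30% | 0.20/0.70 = 28.6% |
| 20% | 0.30/0.80 = 37.5% |

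For illustration, take q as the 7%–11% ventilation rate that Section 1.1 quotes for hospitalized influenza (assumption). At the cap, 0.45 + 0.55 × 0.07 = 48.9% and 0.45 + 0.55 × 0.11 = 51.1% would ever be ventilated, on either side of one half.

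*Behaviour near the break-even.* With 67 of 150 on PPV at entry, the chance that an arm has at least 76 ever ventilated is 0.02 at q = 5%, 0.13 at 7%, 0.57 at 11% and 0.89 at 15%. With no drug effect and independent arms, exactly one of two arms passes that mark with probability 2 × 0.13 × 0.87 = 23% at q = 7% and 2 × 0.57 × 0.43 = 49% at q = 11%. The contrast then depends on a count crossing a threshold, not on length of ventilation.

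**Reading 2: users only.** The medians are positive. They rest on about 0.45 × 150 = 67 patients per arm at the cap (more if oxygen patients progress) and about 40 ICU patients at 27%. Section 3.3.3 treats later PPV and later ICU entry as outcomes, so these subsets are formed partly after randomization. Only patients on PPV at randomization are a subset fixed at baseline and balanced by stratification (Section 4.2).

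**The case against.** A reader might infer that both medians will be 0 in both arms whatever the drug does, so that the two objectives cannot be answered. The documents do not support that, for four reasons.

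- No section scores non-users as 0 days.
- The 45% limits PPV at entry, not ever-use. At the cap, 9.1% progression brings ever-use to 50%.
- The 27% supports the argument for unmet need and is not a planning assumption. The database's PPV mix is unknown.
- The objectives are to measure duration, in a study that Section 6.1 describes as estimation and hypothesis generation. A user-only median does describe duration.

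All four stand, and they limit the conclusion.

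It can also be said that the plan already covers part of this. Progression to PPV and ICU counts within clinical failure, but as parts of a composite. Section 6.4.3 allows subgroups by stratification factor, but only for selected secondary endpoints, and these durations are not named. Section 6 defers detail to a later SAP, but the protocol has already fixed the median and the population. Kaplan-Meier and Cox methods do not help, since non-users must either enter at time 0 or be dropped. Transformation for analysis of covariance cannot remove a large mass of zeros.

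**Conclusion.** The point holds as a gap in definition for which neither natural reading works well. With non-users at 0 days, the ICU median is 0 in every arm at 27% use. The ventilation median is 0 unless PPV enrolment is close to the cap and progression reaches the break-even, and near the break-even it is driven by a threshold. With users only, the median is descriptive and is not a randomized comparison. The direction and size of the resulting bias cannot be stated from the documents.

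The zero result rests on scoring non-users as 0, about 150 patients per arm, and the background ICU rate carrying over to the trial. These are secondary endpoints, so correcting them is an inexpensive improvement and does not put the design in doubt.

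The text reviewed is Version 3. Version 5 adds a third arm and its statistical section is not in the supplied text, so the wording and the per-arm numbers should be confirmed there.

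**What to change.** - **Ventilation:** report duration among patients on PPV at randomization, by arm, and the proportion newly needing PPV among those on supplemental oxygen at randomization.
- **ICU:** report duration among patients in ICU at randomization and the proportion newly admitted among the others. ICU status at randomization is fixed at baseline but is not a stratification factor, so balance is not assured.
- **User-only medians:** keep them if wanted, labelled as descriptive.
- **All-patient summary, if wanted:** replace the median with mean support days, or ventilator-free and ICU-free days, over a fixed window, with a bootstrap interval for a difference in means. State a rule for deaths, so that early death is not credited as fewer support days. Section 3.2.2 cites mortality of 9%–32%, so the rule matters. The durations within baseline groups need a death rule too.
- **Timing:** write the denominators and rules down before any unblinded efficacy look. Section 3.1.2 has a study biostatistician unblinded on the monitoring committee.

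The cost is a change of summary and denominator on data that the endpoints already require. Precision falls, because ventilation duration would rest on at most about 67 patients per arm at the cap, and ICU duration on the baseline ICU group, whose size the documents do not give.
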